2. INTRODUCTION

The purpose of this statistical analysis plan is to outline the proposed statistical analysis methods for protocol A0081096. This analysis plan provides additional details concerning the statistical analyses that were originally outlined in the study protocol A0081096 dated December 12th 2012, and the subsequent amendment of the protocol dated December 15, 2015.

Pregabalin (Lyrica®) has been approved in over 130 countries to date for varying neuropathic pain indications and for adjunctive treatment of patients with partial seizures and for generalized anxiety disorder. Lyrica is approved in the United States for management of neuropathic pain associated with diabetic peripheral neuropathy or postherpetic neuralgia, for the adjunctive treatment of adult patients with partial onset seizures, and for management of fibromyalgia. Lyrica is approved in European Union countries for the treatment of peripheral neuropathic pain, adjunctive treatment of partial seizures with or without secondary generalization, and for the treatment of generalized anxiety disorder.² Since initial market approval of Lyrica in 2004 through 2014, it is estimated that more than 28.5 million patient years of exposure will have accumulated worldwide. More detailed information, including efficacy results in adults and the possible risks associated with administration of pregabalin, can be found in the current Investigator Brochure (IB).

Prospectively planned ophthalmologic assessments, including visual acuity testing, formal visual field testing and dilated fundusoscopic examination, were performed in the pregabalin clinical development program for all of the initial indications.

Formal visual field testing was conducted in over 2400 patients treated with pregabalin for neuropathic pain, chronic pain syndromes, intractable epilepsy, or generalized anxiety disorder in randomized controlled clinical trials of up to 3 months in duration and in over 3600 patients in open-label trials of up to 4 years in duration. Ophthalmologic assessments were included in the program due to concerns expressed at the time on emerging reports of visual field disturbances with the anticonvulsant vigabatrin, a gamma-aminobutyric acid (GABA)-transaminase inhibitor. The mechanism of the visual field defects with vigabatrin is unknown but was considered as possibly related to its GABA mechanism. As a structural derivative of GABA, regulatory agencies considered similarity of pregabalin to vigabatrin as possible. Subsequently, it became clearer that the mechanism of action of pregabalin was not related to GABA-transaminase inhibition or to a GABA related mechanism. While the mechanism of action of pregabalin is not completely understood, results in animal models indicate that binding to the alpha-2-delta subunit of voltage-gated calcium channels may be involved in the activity of pregabalin.

[figure not shown]
In controlled pregabalin studies, a higher proportion of patients treated with pregabalin reported blurred vision (6%) than did patients treated with placebo (2%), which resolved in the majority of patients during treatment. In patients assessed with prospectively planned ophthalmologic testing, visual acuity was reduced in 7% of patients treated with pregabalin, and 5% of placebo-treated patients. Visual field changes were detected in 13% of

pregabalin-treated, and 12% of placebo-treated patients. Funduscopy changes were observed in 2% of pregabalin-treated and 2% of placebo-treated patients.

This study is a Post-Authorization Safety Studies (PASS). It is being conducted as a commitment agreed upon with the United States Federal Drug Administration (FDA) regulatory agency.

2.1. Study Design

This is a Phase IV, multicenter, double-blind, randomized, placebo-controlled trial to measure visual field sensitivity in subjects with partial epilepsy dosed with pregabalin or placebo. Pregabalin will be dosed at 300 mg/day for 11 weeks after one-week initiation with 150 mg/day, followed by one-week tapering of 150 mg/day. Total treatment period will be 13 weeks.

Schedule of Activities

Protocol Activity	Screening	Baseline	Wk 0 Randomization	Wk 1	Wk 6	Wk 12 (Or ET)	Week 15 (Follow-Up)
Visit Number ⁿ	1	2	3 ^m	4	5	6	7
Informed Consent	X						
Inclusion/Exclusion Criteria	X	X	X				
History/Diagnosis/Demographics	X						
Physical Examination ^p	X					X	
Concomitant Medication	X	X	X	X	X	X	X
Body Weight	X	X		X	X	X	X
Vital Signs (Sitting BP/HR)	X	X		X	X	X	
ECG (Singlet)	X						
EEG	X ^a						
CT or MRI	X ^b						
Clinical Laboratory	1) Hematology ^c	X				X	
	2) Chemistry ^d	X				X	
	3) Urinalysis ^e	X				X	
Urine Pregnancy Test ^f	X					X	
Urine Drug Screen	X						
Ophthalmic Examination	1) External Eye Exam	X				X	X ^g
	2) ETDRS Acuity	X	X			X	X ^e
	3) Intraocular Pressure	X					
	4) Dilated Funduscopy	X					
	5) VFT (24-2 SITA)	X ^{h,l}	X ^{h,l}			X ^h	X ^h
Patient assessment of seizure frequency						X	
Investigational product Dispensing			X ^{i,j}	X ^k	X ^k	X ^j	
Sheehan-Suicidality Tracking Scale (S-STSS) ^{o,r}	X	X	X	X	X	X	X
Columbia-Suicide Severity Rating Scale (C-SSRS) ^{o,r}	X	X	X	X	X	X	X
Suicidal Behaviors Questionnaire – Revised (SBQ-R) ^r	X						
Patient Health Questionnaire–8 (PHQ-8)	X						
Assessment of need to complete a risk assessment ^f	X	X	X	X	X	X	X
Adverse Events Report	X-----X						

-
- a. Subjects who have not had a test within 2 years. See inclusion criteria 1.
 - b. Subjects who have not had a test within 3 years. See inclusion criteria 4.
 - c. Hemoglobin, hematocrit, RBC count, WBC count, platelet count.
 - d. Electrolytes (Na, K, Ca, Cl, bicarbonate), creatinine, BUN, glucose, AST, ALT, alkaline phosphatase, bilirubin, CK, uric acid, albumin, total protein.
 - e. Specific gravity, PH, Glucose (qualitative), Protein (qualitative), Blood (qualitative), Ketones, Nitrite and Microscopy if urine dipstick is positive for blood or protein.
 - f. Childbearing potential female subjects only.
 - g. Subjects who have had visual findings on Week 12 and subsequently confirmed.
 - h. A repeat may be necessary upon the confirmation from central reader.
 - i. Recommend subject to take first dose in the evening.
 - j. Titration/tapering dose.
 - k. Treatment dose.
 - l. Conduct 2 tests.
 - m. Usually occur between the 3rd – 7th day after Baseline (Visit 2) when the verification of VFT is available.
 - n. Screening procedures can be completed within 21 days prior to Baseline; Study Visits 4 – 7 have a ± 3 days window.
 - o. The “Lifetime” assessment is completed at Screening and the “Since Last Visit” assessment is completed at **all** other visits.
 - p. Including neurological exam at screening.
 - q. A risk assessment must be performed and documented if the subject meets the criteria detailed in Protocol.
 - r. Subjects screened/randomized under Amendment 3 will continue the S-STS for assessment of suicidal ideation and behaviour. Subjects screened/randomized under Amendment 4 will have suicidal ideation and behaviour assessed by the C-SSRS and the SBQ-R.

2.2. Study Objectives

The objective of the study is to evaluate visual fields in subjects with partial epilepsy receiving 12 weeks treatment of pregabalin compared to placebo.

2.3. Statistical Power and Sample Size Considerations

The study will be powered to show non-inferiority of pregabalin with respect to placebo on the mean deviation score from the Humphrey threshold test, a secondary endpoint.

Non-inferiority from placebo will be declared with respect to mean deviation if the lower bound of the 95% 2-sided confidence interval of the difference in mean deviation scores between pregabalin and placebo is greater than -2.0 decibels (dB). Assuming the mean deviation scores to be equal and assuming estimated common standard deviation of 1.3 dB, then the proposed sample size of 187 subjects will provide greater than 85% power to show non-inferiority of pregabalin to placebo.

The estimated common standard deviation of 1.3 dB, from the 15 March 2019 dataset prepared for the annual Internal Review Committee (IRC) blinded review (refer to Section 9.6), was used to re-estimate the sample size for the secondary endpoints. Previously, at the time of study design, a common standard deviation of 5.6 dB had been used for the sample size determination based on literature.² Table 1 below used common standard deviation (1.3) and the number of enrolled subjects (n=187) to estimate the study power.

Table 1. Study 1096 Sample Size and Power for the Secondary Endpoint

Total Number of enrolled subject	Common Standard Deviation	Non-inferiority Margin	Power
187	1.3	-2.0	>99.9%

For the primary endpoint, the proposed sample size will provide >99.9% power to show non-inferiority of pregabalin to placebo with respect to the proportion of subjects with a repeated decrease in the same 5 visual field points, with non-inferiority declared if the upper bound of the 95% confidence interval for the difference between pregabalin and placebo does not exceed 10% and assuming a proportion of subjects meeting primary endpoint definition of 1% for both groups. Table 2 below provided the estimated power for the primary endpoint.

Table 2. Study 1096 Sample Size and Power for the Primary Endpoint

Total Number of enrolled subjects	Proportion of Subjects Meeting Primary Endpoint Definition	Non-inferiority Margin	Power
187	1%	10%	>99.9%

3. INTERIM ANALYSES, DATA MONITORING COMMITTEE, FINAL ANALYSES AND UNBLINDING

No interim analysis has been planned for this study.

This study will use an Internal Review Committee (IRC).

The IRC for this study will be independent of the study team and will not be involved in the conduct of the study otherwise. The Pfizer colleagues comprising the independent IRC and their responsibilities will be defined in an IRC Charter. The IRC will be responsible for ongoing monitoring of the safety of subjects in the study according to the Charter. Communication between the IRC and the Study Team will be from the IRC Chair to the clinical lead or delegate to the Study Team. The possible IRC recommendations and the method of communicating the IRC recommendations will be stated in the Charter.

The final analyses will be performed after requirements for final release of the randomization codes have been met, and the official database is released.

4. HYPOTHESES AND DECISION RULES

4.1. Statistical Hypotheses

The null hypothesis is that the proportion of patients with deterioration in the pregabalin group is greater than or equal to 10% higher than in the placebo group. The alternative hypothesis is that the difference in proportions (pregabalin minus placebo) is less than 10%. That is:

$$H_0: \pi_{PGB} - \pi_{PBO} \geq 10\%$$

$$H_a: \pi_{PGB} - \pi_{PBO} < 10\%$$

In these hypothesis statements π is the parameter for the proportion of patients with deterioration in the respective treatment group.

4.2. Statistical Decision Rules

The difference in proportions between pregabalin and placebo will be compared using a 2-sided 95% confidence interval (CI). Non-inferiority will be demonstrated if the upper CI bound is less than 0.10 (10%).

5. ANALYSIS SETS

5.1. Full Analysis Set

The Full Analysis Set (referred to in the protocol as the intent-to-treat (ITT) population) is defined as all subjects randomized to treatment who received at least one dose of study medication.

Since data will not be imputed for patients who do not have a baseline or for patients who do not have post-baseline data for a specific parameter, such patients will not appear in the FAS analyses for that parameter. Subjects who had a decrease in at least 5 points at termination but did not return for a repeat test will be included in the FAS set and will be assumed to have a confirmed decrease for VFT analysis. Termination is the VFT performed at Week 12 or the last available post-treatment VFT for subjects who did not complete the study (per Protocol Section 9.4.1).

5.2. 'PER PROTOCOL' Analysis Set

The primary analysis will be performed on the Per Protocol population.

The Per Protocol population is a subset of the ITT population, and excludes subjects who had a decrease in at least 5 points at termination but did not return for a repeat test. The Per Protocol population may also exclude subjects with major protocol violations; the list of subjects excluded will be determined prior to breaking the blind. The expectation is that the PP subset will be close in the number of subjects to the to the number of subjects randomized.

5.3. Safety Analysis Set

In this study, all parameters to be analyzed are safety parameters. The primary analysis of the primary parameter will be performed using the Per Protocol population, with a supplementary analysis that uses the ITT population. All other safety data will be summarized using the ITT population.

5.4. OTHER ANALYSIS SETS

Not applicable.

5.5. Treatment Misallocations

Subjects who were:

- Randomized but not treated are not in the ITT population and will thus be excluded from all safety summaries.
- Randomized but took incorrect treatment will be reported under the treatment actually received for all safety summaries.

5.6. Protocol Deviations

The list of protocol deviations will be compiled prior to database closure. Subjects who *had a decrease in at least 5 points at termination* (the Week 12 VFT or last available post-treatment VFT) *but did not return for a repeat test* will be excluded from the Per Protocol population, as will patients with certain protocol deviations (to be determined based on clinical judgment prior to breaking the blind).

6. ENDPOINTS AND COVARIATES

6.1. Efficacy Endpoint(s)

Not applicable, as this is a safety study without efficacy endpoints.

6.2. Safety Endpoints

Primary Endpoint:

The primary endpoint is the proportion of subjects with a decrease in the threshold value from baseline to termination in any five or more points (in either eye) at the $p < 0.05$ level repeated in the same five points on subsequent computerized automated perimetry testing (Humphrey 24-2 SITA standard).

The primary endpoint is derived from the Humphrey 24-2 SITA Standard visual field analyzer. For each eye there are 52 test points. For each test point, the Humphrey analyzer determines the threshold value for sensitivity to light by the subject. In addition, for each of the 52 points, the test provides probabilities ($p < 0.05$, $p < 0.02$, etc) that a patient with normal vision of the same age would have the same result, ie, that the measured value at that point was at or below the respective percentile of the age-specific empiric distribution at that position of the field for normal subjects. For each of the 52 test points for each eye, the data received from the Central Reader will contain a 1 if $p < 0.05$ or a 0 otherwise. (see [Appendix A.1.2](#)).

The primary endpoint (proportion of patients with deterioration) is determined as follows: Baseline and all other visits for visual field test (VFT) will be based on the visits defined by the central reader. There are 2 tests performed for the Screening visit, these values will not be used for baseline determination. A point will be considered abnormal at baseline only if it was abnormal ($p < 0.05$) at both baseline tests. A patient with 5 or more points that are $p < 0.05$ at termination (ie, a value of 1 in the database) that were not significant (a 0 in the database) at baseline is required to have a repeat test. If at the repeat test 5 or more of the same points are $p < 0.05$, then that patient is considered to have deterioration. This assessment is done separately for each eye, and a patient is considered to have deterioration if this is true for either eye.

Secondary Endpoints:

Mean Deviation (MD) is a global index of visual field depression. The MD ranges from 0 decibels (dB) (no defect) to about -32 dB (end-stage damage). *Change in mean deviation from baseline to termination will be computed for each subject.* Baseline and all other visits for mean deviation will be based on the visits defined by the central reader and study treatment dates. *Baseline mean deviation will be the average of the two mean deviations from the Baseline visit, and termination will be the mean deviation at the Week 12 visit (or the last post-treatment values available after Day 1 for subjects who terminate early). If a repeat test was done at termination, the mean deviation from the repeat test will be used. For each subject, the worst eye (ie, the eye with the greatest decrease in mean deviation) will be used in the analysis.*

The best corrected visual acuity (with glasses or best possible glasses prescription) will be measured using the Early Treatment Diabetic Retinopathy Study (ETDRS) charts. The letters on chart A are read using the right eye and chart B using the left eye. The subject starts at the top of the chart and begins to read down the chart. The subject reads down the chart until they reach a row where a minimum of three letters on a line cannot be read. The subject is scored by how many letters could be correctly identified. Details of visual acuity scoring have been defined in Appendix A.1.3. Change in visual acuity from baseline to termination will be computed for each subject. Baseline will be defined as the last visual acuity assessment prior to receiving study medication, and termination will be the visual acuity assessment at the Week 12 visit (or the last post-treatment assessment available after Day 1 for subjects who terminate early). If acuity was assessed at a repeat visit at termination, the acuity from the repeat test will be used. For each subject, the worst eye (ie, the eye with the greatest decrease in visual acuity) will be used in the analysis.

Other Safety Endpoints:

Other safety parameters, including adverse events, physical examination results, vital signs, body weight, clinical laboratory results, and subject assessment of seizure frequency as compared to before taking study medication. Sheehan Suicidality Tracking Scale (S-STSS), and Columbia Suicide Severity Scale (C-SSRS) will be summarized by treatment group, but not analyzed inferentially. For subjects who randomized prior to Amendment 4, -STS will be mapped to Columbia-Classification Algorithm of Suicide Assessment (C-CASA) and for subjects who randomized after amendment 4, C-SSRS will be mapped to Columbia-Classification Algorithm of Suicide Assessment (C-CASA) before being analysed.

Any adverse events (AE) occurring following start of treatment should be counted as treatment emergent. Events that occur in a non-treatment period after treatment was initiated (for example, washout or follow-up) will be counted as treatment emergent and attributed to treatment.

6.3. Other Endpoints

Screening ophthalmologic assessment (Dilated Funduscopy), SBQ-R and self-administered Patient Health Questionnaire (PHQ-8) will be summarized for both treatments combined and by treatment group. For subjects who require Mental Health Risk Assessment (MHRA), it may be assessed at screening, baseline and post treatment, eg, for those subjects who require evaluation.

6.4. Covariates

The covariate for Mean Deviation is the baseline MD, which is the average of the two mean deviations from the Baseline visit.

The covariate for Visual Acuity is the baseline visual acuity, defined as the last visual acuity assessment prior to receiving study medication.

7. HANDLING OF MISSING VALUES

For each endpoint, if the Week 12 test is missing then the last available post-treatment test after Day 1 will be used, eg, a last observation carried forward (LOCF) approach will be taken. *Data will not be imputed for subjects who do not have any VFTs or visual acuity tests after baseline* or for subjects who do not have a baseline; rather such subjects will not contribute to the analysis of that endpoint.

Subjects who *had a decrease in at least 5 points at termination but did not return for a return test* will be excluded from the Per Protocol set. In the analysis of the ITT population, such patients will be assumed to have a confirmed decrease.

8. STATISTICAL METHODOLOGY AND STATISTICAL ANALYSES

8.1. Statistical METHODS

The primary analysis will compare the difference in proportions for the primary endpoint (based on a 2x2 contingency table combined across centers) using a 2-sided 95% confidence interval. Because it is expected that the proportions will be small for each treatment group, unconditional exact methods (StatXact or Proc-StatXact)² will be used to compute the confidence interval. Or the following code may be used.

```

/***
*** Hypothetic Example of calculated Exact approximation 95% CI
*** where there are 4 cases of deterioration and all 4 belong to PGB
***/

%macro pairs(x1px2=,nper=);
%do x1=0 %to &x1px2;
  data a;
  x2=&x1px2 -&x1;
  r=0; d=1; w=&nper-&x1; output;
  r=1; d=1; w=&x1; output;
  r=0; d=2; w=&nper - x2; output;
  r=1; d=2; w=x2; output;
run;
proc freq data=a;
```

```
tables d*r / norow nocol nopct exact riskdiff(cl=newcombe);  
exact riskdiff(method=score);  
weight w;  
output out=diffs riskdiff;  
  
run;  
  
data diffs2; set diffs;  
  
keep x1 n1 x2 n2 _rdif2 _x1_rdif2 xu_rdif2;  
x1=&x1; n1=&nper; x2=(&x1px2 - &x1); n2=&nper;  
  
run;  
  
proc append base=pairvary data=diffs2; run;  
  
%end;  
  
%mend pairs;  
  
*****;  
  
%pairs(x1px2=4,nper=142); * where there are 4 cases of deterioration  
and all 4 belong to PGB  
  
run;
```

Continuous measures (MD, visual acuity) will be analyzed using an ANCOVA main effects model, with treatment and study center in the model and the respective baseline score as a covariate. Output from the ANCOVA models will include adjusted (least squares) means and standard errors for each treatment group, p-values for the pregabalin versus placebo comparison, and 95% confidence intervals on the difference in LS means between pregabalin and placebo.

The only time point analyzed is Week 12 (or last observation, for patients who terminate early). Ophthalmologic data collected at Week 6 and follow-up will be summarized descriptively but not analyzed inferentially, unless it is used as the termination time point in the primary analysis

Centers with fewer than 4 patients will be combined with other centers prior to breaking the blind. Centers with 4 or more patients may be combined with other centers as needed, or may be left as separate centers. The pooling will be done geographically if possible. These pooled centers will be used in place of center in the analyses that include center in the model.

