3. TRIAL DESIGN

This is a Phase IV, multicenter, double-blind, randomized, placebo-controlled trial to measure visual field sensitivity in subjects with partial epilepsy dosed with pregabalin or placebo. Pregabalin will be dosed at 300 mg/day for 11 weeks after one-week initiation with 150 mg/day, followed by one-week tapering of 150 mg/day. Total treatment period will be 13 weeks. Comprehensive ophthalmologic testing will be done at pre-treatment baseline to exclude subjects with pre-existing eye disease.

A central reader will assure the quality of all visual field test results with pre-specified criteria. Any field failing this quality assurance criteria either due to poor subject compliance or due to failure to follow testing procedures will be repeated as soon as possible within 2 weeks following notification from the central reader. Prior to randomization subjects must

meet the pre-specified quality assurance criteria. Subjects failing to meet this criteria at Baseline either due to poor subject compliance or due to failure to follow testing procedures can be re-screened one additional time after 3 months and will keep their previously assigned ID number. Rescreening may also be allowed for subjects with non-lesional epilepsy who may have been screen failed for reasons other than those specified above, if correctable.

Approximately 187 subjects will participate in the study. Subjects will be randomized 1:1 to pregabalin or placebo, with approximately 93 randomized to pregabalin and 93 to placebo.

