4	Feb 16, 2016	PPD [REDACTED]	
As of protocol amendment, dated December 15, 2015 the following changes has been incorporated:
 
 1. The Sheehan Suicidality Tracking Scale has been replaced by the Columbia Suicide Severity Rating Scale (C-SSRS), For subjects who randomized prior to Amendment 4, S-STs will be mapped to Columbia-Classification Algorithm of Suicide Assessment (C-CASA) and for subjects who randomized after amendment 4, C-SSRS will be mapped to Columbia-Classification Algorithm of Suicide Assessment (C-CASA). 2. SBQ-R has been added at screening. 3. Core Data Sheet (CDS) has been replaced by Investigator’s Brochure (IB). 4. The schedule of activities and introduction text have been updated accordingly. 5. To be consistent with new version of the protocol, some wording has changed in the introduction section of this SAP and other section. 6. Additional SAP amendment not related to protocol 4th amendment: 
 • Mental Health Risk Assessment (MHRA); • Added the SAS code for primary endpoint.
5	Sep 30, 2020	PPD [REDACTED]	
 1. Per protocol amendment (amendment 5) and adjusted the sample size and power of the study using the observed mean deviation (MD) common standard deviation (SD = 1.3) from a 15 March 2019 dataset prepared for the annual IRC review. 
Common SD changed from 5.6 dB from literature¹ at the time of design of the study to observed common SD 1.3 dB

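### The SAP's optional code for the primary confidence interval allows only one sample size for both arms, and its example call still uses the superseded 142 per arm

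*SAP*

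**What the plan says.** SAP section 8.1 bases the primary analysis on a 2x2 table pooled over centers. It specifies a two-sided 95% interval by unconditional exact methods in StatXact or Proc-StatXact, and then adds "Or the following code may be used". The amendment table in SAP section 1 (version 4) lists this code as "Added the SAS code for primary endpoint".

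The code carries the comment "Hypothetic Example of calculated Exact approximation 95% CI" and describes its case as one "where there are 4 cases of deterioration and all 4 belong to PGB". The macro has two arguments, the total number of events and nper. It loops over every split of that total between the arms. Both rows of each table are built from nper, and the output step records "x1=&x1; n1=&nper; x2=(&x1px2 - &x1); n2=&nper;". The call is "pairs(x1px2=4,nper=142".

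The current design is smaller. SAP section 2.3 says that "the proposed sample size of 187 subjects will provide greater than 85% power" for mean deviation, and Protocol section 3 describes 1:1 randomization "with approximately 93 randomized to pregabalin and 93 to placebo". The figure of 284 subjects, 142 per arm, survives only in the amendment histories in Protocol Appendices 3 and 4.

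SAP section 8.2.1 makes the Per Protocol set primary, with non-inferiority if the upper limit is below 10%. SAP section 5.2 removes subjects who showed a decrease but had no repeat test, and may remove major protocol violators. SAP section 7 drops subjects with no field test after baseline.

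**The concern.** The primary conclusion of this safety study rests on one upper limit compared with 10%. The SAP offers two routes to that limit, and they are not equivalent.

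StatXact takes each arm's own denominator. The macro cannot. Equal arms are unlikely: 187 is an odd total, and the exclusions listed above need not fall evenly. An analyst who updates nper to a plausible value such as 93 gets a clean run and a plausible limit that does not belong to the observed table. If the count is near the decision boundary, the choice of route can decide the result.

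The leftover 142 is a separate and simpler matter. SAP version 5 revised the sample size in section 2.3 and did not carry the change into the example.

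**Working it through.** **Inputs.** Example: 4 pregabalin events, 0 placebo events, nper=142 (SAP 8.1). Current size: 187 in total, about 93 per arm (SAP 2.3, Protocol 3). Margin 10%, two-sided 95% interval (SAP 8.2.1). Assumed event rate 1% in both arms (SAP 2.3). The documents give no Per Protocol arm sizes, so the unequal splits below are assumptions.

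**1. The plan's own figures.** Normal-approximation power for the primary endpoint with n = 93 per arm is Φ(0.10/√(2 × 0.01 × 0.99/93) − 1.96) = Φ(6.85 − 1.96) = Φ(4.89), which agrees with the stated >99.9%. Under the exact rule with 93 and 94 subjects, power is 99.3%.

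The origin of 142 can also be recovered. With the former SD of 5.6 dB, a margin of 2.0 dB and 85% power, n = 2 × 5.6² × (1.960 + 1.036)²/2.0² ≈ 140.8, so 141 per arm. At 142 per arm the power is 85.3%. The 142 is therefore the old design figure.

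**2. The SAP's example at old and current size.** The exact upper limit comes from inverting the one-sided 2.5% score test for the difference, maximised over the nuisance rate. This is the method the code requests. The Newcombe limit is a hand check: with no placebo events it equals the Wilson upper limit for pregabalin, (p + z²/2n + z√(p(1−p)/n + z²/4n²))/(1 + z²/n).

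- n = 142: (0.0282 + 0.0135 + 0.0304)/1.0271 = 0.0702
- n = 93: (0.0430 + 0.0207 + 0.0461)/1.0413 = 0.1054

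| 4 v 0 | Exact upper limit | Newcombe | Against 10% |
|---|---|---|---|
| 142 per arm | 7.06% | 7.02% | pass |
| 93 per arm | 10.65% | 10.54% | fail |

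With no placebo events, the largest passing pregabalin count is 7 at 142 per arm (9.89%) and 3 at 93 per arm (9.25%).

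**3. The single n, after 142 has been updated.** Both splits below add to 187.

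| Assumed table | Correct exact limit | nper=93 | nper=94 |
|---|---|---|---|
| 4/90 v 1/97 | 10.17% (fail) | 9.67% (pass) | 9.61% (pass) |
| 5/97 v 2/90 | 9.67% (pass) | 10.33% (fail) | 10.19% (fail) |

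The error favours pregabalin in the first row and counts against it in the second. Rounding nper up or down does not matter.

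**4. When the decision does not change.** For 4 v 1, the limit is 9.80% at 92/94 and 9.95% at 91/93. Both pass, as they do with nper=93.

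**5. How often this region is reached.** If the true rate is 1%, the chance of 4 or more events among 93 pregabalin subjects is 1 − P(X ≤ 3) with X ~ Bin(93, 0.01), about 1.4%.

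**The case against.** The code is an illustration. Its heading says so, it reads no trial data, it lists every split of an invented event total, and nper is a typed argument. The governing text comes first and is sound: StatXact on the real 2x2 table, Per Protocol set, limit below 10%. For 142 to reach the result, someone would have to enter the observed events, leave 142 in place, and overlook 284 subjects in a trial of about 187. The SAP prints no limit for the example, so no stated result is wrong. SAP section 5.2 expects the Per Protocol set to be close to the number randomized, small imbalances leave the decision alone, and at a 1% event rate the boundary is seldom reached.

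Most of this stands, and it disposes of 142 as a serious threat. It does not dispose of the single n. The SAP permits the code for the primary interval, and its change log presents it as the code for the primary endpoint. Updating nper does not let unequal arms be entered. PROC FREQ itself would accept them; the data step that feeds it does not.

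**Conclusion.** The point holds as a defect in a permitted but secondary route to the primary interval. As written, the macro cannot represent unequal arms, and near the 10% margin it can disagree with StatXact in either direction. In the two assumed splits the limit shifts by about 0.5 and 0.7 percentage points, enough to reverse the decision. This rests on Per Protocol splits of 90 and 97, which are assumed, and on counts that are improbable at the planned 1% rate.

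A reader might infer two stronger things. One is that the analysis is planned with 142 per arm. If 142 were left in with 93 and 94 real subjects, the chance of passing at true rates of 11% v 1% would be about 22% instead of 1.7%. The documents do not support this as a description of the plan: the call is labelled hypothetical and StatXact is named first. The other is that wrong denominators always make the limit too small. That is true of 142 but not of the single n, as the second assumed split shows.

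The correction should be made before unblinding.

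**What to change.** In SAP section 8.1:

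- Replace nper with separate n1 and n2, set to the subjects in each arm with an evaluable outcome, first for the Per Protocol set and then for ITT.
- Run the code on the single observed table instead of looping over every split of the event total.
- Remove 142, or restate the example at about 93 per arm.

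The cost is a few lines of code and wording. The method, margin and analysis sets do not change. With those changes the macro is set up from the same table as StatXact, so the choice of software should no longer affect the decision. If the 4 v 0 example is restated at 93 per arm, it will show a limit above 10%.
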